#### 5.4 Dose Tapering at End of Treatment/Discontinuation

Patients whose cGVHD has not progressed at the time of study treatment completion or discontinuation of combination treatment of belumosudil and ruxolitinib, for reasons other than AEs, should be tapered off belumosudil by reducing the dose every 2 weeks (14 days) as described below:

Starting dose of 200mg BID belumosudil → 200mg QD → 200mg QOD → Discontinue

---

---

**OR**

Starting dose of 200mg belumosudil QD → 200mg QOD → Discontinue

The belumosudil tapering process is to be initiated following the end of the 13 cycles of treatment (i.e., at EOT), and should last 4 weeks.

Tapering of ruxolitinib should be done slowly as per the product monograph, with documented CR or PR for at least 2 months, starting with a 50% dose reduction every 2 months (56 days). Initial dose reduction is to 5 mg orally BID. If sustained cGvHD response is observed (i.e. no worsening of cGvHD signs and symptoms), patient is further tapered by a second 50% dosage reduction to 5 mg orally QD for an additional 2 months (56 days), prior to cessation. The tapering process can be initiated prior to the EOT visit if the patient is responding well.

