## **2. STUDY DESIGN**

This is a phase II non-randomized, open-label study in patients with moderate to severe cGvHD who have failed to respond to, or are intolerant of first line therapy. Patients will receive combination therapy with two oral agents (belumosudil, ruxolitinib) with documented individual efficacy as second line in cGVHD treatment. A maximum of 63 participants are expected to be enrolled in Canada.

[figure not shown]
Participants will begin on 10 mg BID of oral ruxolitinib alone for one cycle (i.e. Cycle 1). Each cycle is equal to 28 days. Starting at cycle 2, they will take belumosudil in addition to ruxolitinib, at a dose of 200 mg OD or 200 mg BID (if on a PPI). Patients will remain on dual therapy for 48 weeks (i.e. 12 cycles), until progression of cGVHD, or intolerance to either agent, whichever occurs sooner. A safety visit will be conducted at the end of treatment, 28 days following end of treatment, as well as a remote follow up visit conducted 24 weeks following end of treatment.

The end points will include overall response rates at 24 weeks on treatment and failure-free survival at 48 weeks on treatment (i.e., 28 and 52 weeks on combination therapy) which adopts composite endpoints including: (1) requirement of additional treatment or switch over, (2) progression or flare-up of GvHD with/without ruxolitinib tapering, and (3) death from relapse/non-relapse mortality.

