- In the event that at the intended C2D1 visit assessment the participant is experiencing Grade  $\geq 3$  AE(s), treatment with belumosudil should not begin. This visit will be considered an unscheduled visit and the C2D1 visit should be rescheduled. The participant can continue on ruxolitinib alone and should be followed for resolution of the Grade  $\geq 3$  AE(s). If the Grade  $\geq 3$  AE(s) improve to Grade  $\leq 2$  or resolve completely within 4 weeks, the participant will still be eligible to receive belumosudil. In this case, they should come back in for a true C2D1 visit and can complete all the necessary assessments as well as belumosudil dosing. If the Grade  $\geq 3$  AE(s) does not recover within 4 weeks, the participant will move on to the End of Treatment visit and discontinue study. If there are any questions or concerns about the patient status and treatment in these scenarios, this should be discussed with the sponsor.
- HIV, HBsAg, HBV DNA, HCV antibody, and HCV RNA.
- Ruxolitinib may continue on past the C13D28 visit as per standard of care and if, in the opinion of the treating investigator, the patient is receiving clinical benefit. Tapering of ruxolitinib should be done slowly as per the product monograph with documented CR or PR, starting with a 50% dose reduction every 2 months (56 days). Initial dose reduction is to 5 mg orally BID. If sustained cGvHD response is observed (i.e. no worsening of cGvHD signs and symptoms), patient is further tapered by a second 50% dosage reduction to 5 mg orally QD for an additional 2 months (56 days), prior to cessation.
- Patients whose cGVHD has not progressed at the time of study treatment completion or discontinuation of combination treatment of belumosudil and ruxolitinib for reasons other than AEs should be tapered off belumosudil by reducing the dose every 2 weeks (14 days) as described below:  
Starting dose of 200mg BID  $\rightarrow$  200mg QD  $\rightarrow$  200mg QOD  $\rightarrow$  Discontinue **OR** Starting dose of 200mg QD  $\rightarrow$  200mg QOD  $\rightarrow$  Discontinue
- For those participants who completed all treatment visits, the C13D28 visit can be considered the End of Treatment Visit.
- Only subsequent therapies used to treat cGvHD need to be captured during the period from the 28-day safety follow up and the 6 month follow up visit

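### Section 5.4 gives one belumosudil taper length, 4 weeks, for two dose ladders that differ by a 14-day step, so it cannot hold for both dose groups

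*Protocol*

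**What the plan says.** Belumosudil is given in two ways, depending on proton pump inhibitor use: "at a dose of 200 mg OD or 200 mg BID (if on a PPI") (Protocol, Section 2). Both starting doses are therefore expected in the trial.

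Section 5.4 covers patients whose disease has not progressed when combination treatment ends, other than those stopping for adverse events. It sets a 14-day interval between reductions and gives two ladders:

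- BID: "Starting dose of 200mg BID belumosudil → 200mg QD → 200mg QOD → Discontinue"
- QD: "Starting dose of 200mg belumosudil QD → 200mg QOD → Discontinue"

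It then gives one timing statement, with no split by starting dose. The taper begins once the 13 cycles are over: "i.e., at EOT), and should last 4 weeks".

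The belumosudil taper footnote in Section 8 repeats the interval ("should be tapered off belumosudil by reducing the dose every 2 weeks (14 days) as described below") and both ladders, but gives no total length. The calendar grid marks the taper in the EOT column.

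**The concern.** Three elements are fixed together: the interval, the number of steps and the total length. Any two of them determine the third once the day of the first reduction is known. The number of steps differs between the dose groups, while the interval and the total are the same for both, so the three do not look compatible.

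This is a dosing instruction for the investigational product. A site can follow the ladder or the stated length in good faith and reach a different last day of belumosudil. That date feeds at least one reporting rule: Section 10.4 requires prompt reporting of any death, whatever the cause, up to 28 days after the final administration of the investigational product. Post-EOT tablet supply and accountability depend on it as well.

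**Working it through.** **Inputs (Protocol, Section 5.4)**

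- Interval between reductions: 14 days.
- Reductions, r: BID ladder r = 3 (BID to QD, QD to QOD, QOD to stop); QD ladder r = 2 (QD to QOD, QOD to stop).
- Stated length for all patients: 4 weeks = 28 days, counted from EOT.

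**Formula**

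Let d be the number of days from EOT to the first reduction. Then taper length = d + 14 × (r − 1).

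**Trying to reproduce the stated 28 days**

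| First reduction | BID (r = 3) | QD (r = 2) |
|---|---|---|
| At EOT (d = 0) | 0 + 14 × 2 = 28 days (4 weeks) | 0 + 14 × 1 = 14 days (2 weeks) |
| 14 days after EOT (d = 14) | 14 + 14 × 2 = 42 days (6 weeks) | 14 + 14 × 1 = 28 days (4 weeks) |

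The 4 weeks is reproduced for BID only in the first row and for QD only in the second. For any common d, the difference between the groups is 14 × (3 − 2) = 14 days, so no common starting rule gives 28 days for both.

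**Consequence for the death-reporting cutoff (Section 10.4, 28 days after the last investigational product dose)**

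The last dose is taken as the end of the final step:

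- QD: 14 + 28 = day 42 after EOT, or 28 + 28 = day 56.
- BID: 28 + 28 = day 56 after EOT, or 42 + 28 = day 70.

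**Consequence for tablets**

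Over 14 days, QOD uses 7 tablets, QD 14 and BID 28.

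- QD starters: 7 tablets (d = 0), or 14 + 7 = 21 (d = 14).
- BID starters: 14 + 7 = 21 tablets (d = 0), or 28 + 14 + 7 = 49 (d = 14).

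**The case against.** The strongest reply is that the two readings are not equally supported. Section 5.4 says the taper is initiated at EOT, and the calendar marks it in the EOT column. A taper that has begun would ordinarily mean that a reduction has been made. On that reading the BID ladder takes exactly 4 weeks, and the duration sentence merely describes the longer ladder without saying so. The ladders and interval are the operative instruction and agree between Sections 5.4 and 8. This stands as the more natural reading of the words. It does not remove the conflict, because QD patients, who are all those not on a proton pump inhibitor, would then finish in 2 weeks against a stated 4. The sentence does not give 4 weeks as a maximum, limit it to BID patients, or set a different first-reduction day for each group.

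A reader might infer more than the document supports:

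- *That one dose group's instruction is shown to be wrong.* It is not. The text shows that length, interval and steps cannot all hold, but not which of them is mistaken.
- *That patients already reduced to QOD are left without a taper.* Table 5 gives discontinuation as the next step below QOD, and both ladders end that way. There is no lower level to step to.
- *That the contraception period and the general adverse-event window also shift.* Contraception runs from the last dose of any study therapy (Section 9.3), and adverse-event reporting from the last dose of study treatment (Section 10.7). Ruxolitinib may continue beyond Cycle 13 and has its own taper in 56-day steps, so in those patients the belumosudil taper need not set either date.
- *That patients who stop early have conflicting dosing.* The mention of 13 cycles is glossed as EOT, and the calendar footnote covers discontinuation as well as completion with no 13-cycle condition. The wording is loose, but no conflicting dose results.

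It is also fair to say that the death-reporting window is counted from each patient's actual last dose, and that doses are recorded in diaries and the eCRF. The window moves with the patient, so the text does not show that any follow-up would be lost.

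**Conclusion.** The inconsistency is real and minor. With 14-day steps and one starting rule, the stated 4 weeks cannot be true for both dose groups: the tapers take 28 days (BID) and 14 days (QD), or 42 and 28. The calendar footnote does not resolve it.

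The size is a 14-day uncertainty, per tapered patient, in belumosudil exposure after EOT and in the last-dose date. The end of the investigational-product death-reporting window moves by the same 14 days. The tablet difference is 14 for a QD starter (21 − 7) and 28 for a BID starter (49 − 21).

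This rests on reading the 4 weeks as the length for every patient, as the sentence is written, and on the first reduction falling either at EOT or one interval later. That sites will in fact diverge is a possibility the wording allows, not something the protocol demonstrates.

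The primary response rate at C8D1, alpha and power are untouched.

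**What to change.** Reconcile the duration sentence in Section 5.4 with the two ladders there and with the calendar footnote in Section 8. For each starting dose, state when the first reduction occurs relative to EOT and the total length that follows, and use the same wording in both places. In the same edit, clarify that the reference to 13 cycles does not exclude patients who stop earlier and whom the section otherwise covers. Which schedule applies is for the sponsor to decide; none is proposed here.

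The cost is a wording change in two places and a check of post-EOT drug supply. No visits or procedures are added.

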### **5.5 Patient Compliance and Dropout**

To the extent possible, patients must strictly follow the continuous daily dosing schedule during the course of study treatment. Patients that skip more than 7 consecutive days of both drugs, in the absence of investigational product related toxicity, will be discontinued from the study unless approved by both the Sponsor and treating Investigator.

Compliance to study medication dosing will be documented using patient diaries and pill counting. Patients will record the date, time and number of pills consumed in the diary on a daily basis. The Principal Investigator (PI) or designee will account for the number of tablets dispensed against those returned by the patient. Any deviations and missed doses will be recorded in the eCRF and drug accountability logs. Reasoning for missed doses should be documented in the patient diaries when possible, as well as within the study drug administration form in the eCRF. The PI / designee will try to ensure complete compliance with the dosing schedule by providing timely instructions to the patients.

### **5.6 Premature Withdrawal/Discontinuation Criteria**

At the discretion of the QI, a patient may be removed from the study for the following reasons:

- Progression of cGVHD as defined by NIH Consensus Criteria
- Noncompliance with study procedures
- Need for treatment with medications, such as a new systemic agent for cGVHD, not allowed by the study protocol
- Recurrence of underlying malignancy, as defined by established disease specific criteria, or other intercurrent illness that interferes with study assessments

- Unacceptable toxicity related to study participation
- Investigator decision.
  - Note that patients should be withdrawn from the study if there has been no response after 12 months of treatment, if in the judgement of the Investigator there has been no clinical benefit for the patient, e.g., in terms of organ score improvements, improvements in Lee symptom scores or reductions of corticosteroid / tacrolimus doses.
- Other treatments become available
- Patient preference / withdrawal of consent or loss to follow-up
- Termination of the study by the sponsor
- Pregnancy in a female participant will lead to definitive treatment discontinuation in all cases.

Patients with a Lack of Response or Mixed response may continue treatment with belumosudil and ruxolitinib, and can remain on study if the treating Investigator considers continued treatment to be in the patient's best interest, but only after approval from the Sponsor and documentation of patient's willingness to continue. The rationale for continued treatment in such instances must be clearly documented. For clarity, Lack of Response or Mixed response will be considered as progression event for analysis purposes.

Patients may withdraw from the study at any time. Patients who discontinue from the study will be encouraged to return to the study site to undergo the evaluations listed for the End of Treatment Visit and for follow-up visits. In the instances where a reason for withdrawal of consent is given, this will be captured in the eCRF. Patient data up to withdrawal of consent will be included in the analysis of the study, and where permitted, publicly available data can be included after withdrawal of consent.

If the reason for withdrawal is the occurrence of an AE, the patient will be followed by the QI until such events resolve, stabilize, and, according to the QI's judgment, there is no need of further follow-up. The reason for withdrawal from the study will be documented in the electronic case report form.

Ozmosis must be notified within 24 hours of a patient's discontinuation from the study.

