There are no prospective studies that have examined the combination of two, non-first line agents in the setting of cGvHD. Therefore, this open-labelled study aims to look at the outcome of combination therapy in an underserved population that is affected by the dual stressors of cGvHD as well as the complications of therapy. There are no uniformly used, nor centrally approved second-line treatments following corticosteroid resistance in cGvHD. Also, practices vary as to the selection of various systemic therapies since to date, no improvement in the high mortality rates has been documented despite treatment with these agents.

Both agents are known to be effective in managing cGVHD but can differ with respect to time to response and mechanisms of action. Ruxolitinib demonstrates efficacy relatively faster due to its anti-inflammatory mechanisms and is therefore useful in mitigating the initial inflammatory processes seen at the onset of cGvHD. It however, does not seem to impact established fibrotic forms of cGvHD to the same degree as belumosudil, which by virtue of its unique mechanism of action, is the only agent currently available that has shown improvement in the organs affected by fibrosis as sequelae of cGvHD. This effect can take longer to establish (as long as 3-6 months) leading to the need for longer durations of steroid or other immunosuppressive therapy. Combining both agents is therefore expected to provide rapid control of the inflammatory process through the use of ruxolitinib and allow sufficient time for the antifibrotic effect of belumosudil to be established leading to better disease control overall without exposing the patient to high doses or prolonged courses of steroids or immunosuppression.

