**Figure 1. Participant treatment schema**

## 3. OBJECTIVES

Primary Objectives	Primary Endpoints
To evaluate efficacy, tolerability and safety of combination treatment of belumosudil with ruxolitinib as second line therapy for steroid-refractory cGvHD.	
 
Efficacy will be assessed using overall response rate (ORR) as per the NIH cGvHD Consensus Response Criteria at 24 weeks of combination treatment (C8D1) of belumosudil with ruxolitinib (i.e., 28 weeks after C1D1).
 
Tolerability and safety will be assessed by the incidence and severity of adverse events (AEs) throughout the treatment duration using CTCAE v5.0 grading.
 

Secondary Objectives	Secondary Endpoints
To evaluate the response achievement with combination treatment of belumosudil with ruxolitinib as second line treatment for cGvHD.	
 
ORR as per the NIH cGvHD Consensus Response Criteria after 48 weeks of combination treatment of belumosudil with ruxolitinib (i.e., 52 weeks after C1D1).
 
Failure-free survival (FFS) after 24 and 48 weeks of combination treatment of belumosudil with ruxolitinib (i.e., 28 and 52 weeks after C1D1). FFS is defined as the time from treatment initiation until the occurrence of treatment failure.
 
Durable response rate in patients who achieve complete or partial response with combination treatment of belumosudil with ruxolitinib as assessed at 52 weeks from
 

	
C1D1. Durable response is defined as sustained improvement in symptoms or absence of disease progression from the time of treatment initiation.
 
4. Overall GvHD symptom burden improvement, serially measured with a modified Lee Symptom Scale (see Appendix D).

Exploratory Objectives	Exploratory Endpoints
To evaluate improvement in musculoskeletal involvement of sclerotic GvHD using the P-ROM score measurement.	1. Changes in the P-ROM score after 12, 24, and 48 weeks of combination therapy in patients who have developed sclerotic GvHD in musculoskeletal involvement of GvHD

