## 9. CONCOMITANT MEDICATIONS

All concomitant medications (including herbal or alternative medicines) taken by the patient from the time of consent through the duration of protocol therapy will be recorded in the eCRF. Initiation of new systemic cGvHD therapy will be considered a new line of treatment and as study treatment failure.

Subsequent cGvHD therapies occurring during the follow up period (24 weeks) will also be captured.

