## 11.3 Evaluation of Study Endpoints

### 11.3.1 Evaluation of the Primary and Secondary Endpoints

Overall response rate (ORR) will be evaluated at 24 and 48 weeks after combination therapy (i.e. 28 and 52 weeks after enrollment), respectively. The proportion of responders and its 95% confidence interval (using exact binomial methods) will be calculated.

Failure-free survival (FFS) will be evaluated using Kaplan-Meier method. The FFS rate will be evaluated at 24 and 48 weeks after combination therapy (i.e. 28 and 52 weeks after enrollment), The composite endpoint of failure is defined as 1) GvHD progression or loss of response requiring switch of systemic GvHD treatment, 2) relapse of primary hematologic disease and 3) non-relapse mortality.

Durable response after response achievement will be evaluated only in the patients achieved CR or PR (any response). The Kaplan-Meier estimate will be calculated from the date of CR/PR achievement to the date of losing response/progression or death from any cause.

GvHD symptom burden improvement, measured serially by the modified Lee Symptom Scale, will be evaluated using repeated measure based on the general linear model. If p-value is less than 0.05, it demonstrates statistically significant change over time within subject.

The Modified Lee symptom score (mLSS) will be used to reflect a symptom burden in cGvHD study patients. The symptoms will be assessed serially and will be evaluated using repeated measure based on the general linear model. If p-value is less than 0.05, it demonstrates statistically significant change over time within subject. The score assesses 7 different organs/areas including skin, eye/mouth, breathing, eating/digestion, muscle/joints, energy, and mental/emotional health. The sum of these domains will be calculated to derive the total mLSS. Clinically meaningful improvement in mLSS is defined as a reduction of  $\geq 7$  points in overall mLSS. Longitudinal change in mLSS is analyzed by repeated measures using generalized linear model over time, evaluating within-subject and between-subject effects. In addition, the proportion of the patients showing clinically meaningful improvement in mLSS is analyzed longitudinally at 12, 24, and 48 weeks. In addition, the best improvement in mLSS is also calculated in each subject and plotted.

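### Failure-free survival is defined by event lists that disagree, and Section 5.6 adds absence of response as a progression event without naming an endpoint or visit

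*Protocol*

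**What the plan says.** Section 3 (repeated in the Synopsis) gives only a time origin and an undefined end: "FFS is defined as the time from treatment initiation until the occurrence of treatment failure".

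Section 2 lists the components as "1) requirement of additional treatment or switch over, (2) progression or flare-up of GvHD with/without ruxolitinib tapering, and (3) death from relapse/non-relapse mortality".

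Section 11.3.1, the statistical section, lists them as "1) GvHD progression or loss of response requiring switch of systemic GvHD treatment, 2) relapse of primary hematologic disease and 3) non-relapse mortality".

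Section 9 adds: "Initiation of new systemic cGvHD therapy will be considered a new line of treatment and as study treatment failure".

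Section 5.6 provides that "Patients with a Lack of Response or Mixed response may continue treatment with belumosudil and ruxolitinib", subject to sponsor approval, and closes that paragraph with "For clarity, Lack of Response or Mixed response will be considered as progression event for analysis purposes". The same section places withdrawal for absence of response at 12 months.

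Table 7 (Section 7.2) defines progression organ by organ as a worsening from the C1D1 baseline. It does not define lack of response or mixed response.

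The landmarks also differ. Sections 3 and 11.3.1 put them 28 and 52 weeks after C1D1 or enrollment. Section 2 describes them as 28 and 52 weeks of combination treatment.

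**The concern.** A time-to-event endpoint needs one list of events. Here a patient can be a failure under one section and failure-free under another. The trial is open-label and single-arm, so an event definition still unsettled when the data are seen leaves room to choose the more favourable one.

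The Section 5.6 sentence makes this worse. It turns the absence of improvement into progression, although Table 7 requires deterioration. It is also unlimited in time. Section 7.2 has response judged at each post-baseline visit, and the Study Calendar marks NIH scoring at weeks 2 and 4. Belumosudil starts only at week 4 (C2D1), and the Study Rationale expects its antifibrotic effect to take up to 3 to 6 months. Read literally, a patient who is stable at week 2 on ruxolitinib alone, or at week 4 on the day belumosudil begins, could already have an event.

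**Working it through.** The protocol states no FFS rate, event count or power, so there is no figure to reproduce. The check compares the definitions and then illustrates how far the choice of text moves the estimate.

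**Step 1: the same patient under each text.** Section 11.3.1 is read with the switch condition attached to both progression and loss of response.

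| Patient | Section 2 | Section 11.3.1 | Section 9 |
|---|---|---|---|
| Progression or flare, stays on both drugs | event | no event | silent |
| Non-fatal relapse, no new cGvHD therapy | no event | event | silent |
| New systemic cGvHD therapy because of intolerance | event | no event | failure |
| Stable disease, stays on both drugs, Section 5.6 applied | event | no event | silent |

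Sections 2 and 11.3.1 disagree in every row.

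**Step 2: week-28 FFS under Section 2 plus Section 5.6.** Input: the overall response rate (ORR) at 6 months is 49.7% under the null and 66% under the alternative (Section 11.1). Assume that every patient is assessed at week 28, and that anyone without CR or PR is classed as lack of response, mixed response or progression. Each non-responder then has an event by that visit, so

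FFS(28) ≤ ORR(28).

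- Alternative: at most 66%, or at least 63 × 0.34 = 21.4 failures among 63 patients.
- Null: at most 49.7%, or at least 63 × 0.503 = 31.7 failures.

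Earlier visits, deaths and switches among responders can only lower this.

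**Step 3: week-28 FFS under Section 11.3.1 with a switch required.** Let s be the share of non-responders who switch. The protocol gives no value, so s is an assumption. Ignoring deaths and relapses,

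FFS(28) = 1 − (1 − ORR) × s.

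| s (assumed) | ORR 66% | ORR 49.7% |
|---|---|---|
| 25% | 91.5% | 87.4% |
| 50% | 83.0% | 74.9% |
| 75% | 74.5% | 62.3% |
| 100% | 66.0% | 49.7% |

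At s = 50% the failures are 63 × 0.34 × 0.5 = 10.7 and 63 × 0.503 × 0.5 = 15.8. The gap from Step 2 is 83.0 − 66.0 = 17 percentage points under the alternative and 74.9 − 49.7 = about 25 under the null. It closes only if every non-responder switches.

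**Step 4: landmarks.** Section 2 limits dual therapy to 48 weeks, so 52 weeks of combination treatment cannot occur. The figures of 28 and 52 weeks fit only when counted from C1D1, with 4 weeks of ruxolitinib alone first: 4 + 24 = 28 and 4 + 48 = 52.

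**The case against.** The best defence is that Section 11.3.1 is the operative definition and Section 2 only a summary. The Section 5.6 sentence closes a paragraph about patients who continue both drugs. Such patients have not switched, so on the natural reading of Section 11.3.1, calling them progressed creates no FFS event. Section 5.6 does not mention FFS at all. It can even help: a switch made for lack of response becomes progression requiring a switch, which brings Section 11.3.1 closer to Section 9 and leaves mainly switches for intolerance uncovered. The landmark wording in Section 2 looks like a slip, since the other sections agree.

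Much of this stands, and it rules out several stronger readings:

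- A reader might infer that Section 5.6 turns every non-responder into an FFS failure. That follows under Section 2, or if the switch condition in Section 11.3.1 qualifies only loss of response. It does not follow on the natural reading.
- A reader might infer that FFS reduces to response at the first assessment, with many patients failing by day 14. The literal text permits an event that early, but the paragraph's context of continuing belumosudil points elsewhere, and the protocol gives no early response rate from which to calculate a figure.
- A reader might infer that mixed response is plainly not progression. The term is undefined. If it means one organ improving while another worsens, Table 7 scores the worsening organ as progression.

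The defence does not remove the conflict. Nothing in the protocol says Section 11.3.1 overrides Sections 2, 5.6 or 9, and Section 5.6 is worded as an analysis rule.

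**Conclusion.** The FFS event definitions are incompatible, and the Section 5.6 sentence is an unrestricted analysis rule that contradicts Table 7. The size of the effect depends on which text governs. Week-28 FFS is at most 66% (alternative) or 49.7% (null) under Section 2 with Section 5.6. It is about 83% or 75% under Section 11.3.1 if half of non-responders switch. The first pair assumes complete week-28 assessment; the second rests on the assumed switch share and ignores deaths and relapses. Neither predicts the trial's result.

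This should be fixed, but it does not threaten the trial's main conclusion. FFS is a secondary Kaplan-Meier estimate with a confidence interval and no decision rule, and success in Section 11.1 rests on ORR alone.

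**What to change.** 1. Use one FFS event list, identical in Sections 2, 3 (with the Synopsis) and 11.3.1 and consistent with Section 9, counted from C1D1: start of any new systemic cGvHD therapy for any reason, relapse of the primary disease, and death from any cause.
2. State whether progression without a switch counts. If it does, define it by Table 7 against the C1D1 baseline.
3. Delete the analysis sentence in Section 5.6, or limit it to a named endpoint and visit so that absence of response alone is not an FFS progression event. Define mixed response in terms of Table 7.
4. Correct the landmarks in Section 2 to 28 and 52 weeks after C1D1.

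The cost is small but not only wording. A reader might assume that all the components are already collected. However, the Study Calendar has no relapse item, Section 10.9 exempts relapse from SAE reporting, and of the FFS components the follow-up visits list only survival status and new cGvHD therapy. A relapse date should therefore be recorded at follow-up for patients who stop treatment early.
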